## Adverse Effects and Reporting

Safety information obtained across two Phase 3 clinical trials of HP/TAZ include the following risks:

- The most common adverse reactions are contact dermatitis (7%), application site pain (3%), folliculitis (2%), skin atrophy (2%), and excoriation (2%). No serious treatment-related AEs were reported but would include severe hypersensitivity reactions and anaphylaxis.
- HP/TAZ contains tazarotene, which is a teratogenic substance. Therefore, HP/TAZ is contraindicated in pregnancy and in this study, all pre-menopausal female subjects must have a negative pregnancy test before enrolling.

- HP/TAZ contains halobetasol propionate, which is a steroid. Therefore, reversible hypothalamic-pituitary-adrenal (HPA) axis suppression may occur, with the potential for glucocorticosteroid insufficiency during or after treatment. Systemic effects of topical corticosteroids may also include Cushing's syndrome, hyperglycemia, and glucosuria. Systemic absorption may require evaluation for HPA axis suppression. Use of potent corticosteroids on large areas, for prolonged durations, under occlusive dressings, or on an altered skin barrier may increase systemic exposure. In addition, the use of topical corticosteroids may increase the risk of posterior subcapsular cataracts and glaucoma. Cataracts and glaucoma have been reported postmarketing with the use of topical corticosteroid products. Advise patients to report any visual symptoms and consider referral to an ophthalmologist for evaluation.
- Some individuals may experience atrophy, striae, telangiectasias, and folliculitis at the application site. If these effects occur, discontinue until the integrity of the skin has been restored. Duobrii® should not be used on eczematous skin, as it may cause severe irritation.
- HPT/TAZ can cause photosensitivity and increase the risk of sunburn. Avoid exposure to sunlight, sunlamps, and weather extremes.
- Skin infections

Unexpected fatal or serious adverse events will be reported to the IRB as soon as possible and no later than 7 calendar days after receipt of the information. Any other unanticipated adverse events will be reported no later than 14 days of receipt of the information.

Pregnancies occurring during the study will be reported no later than 7 days of receipt of information and subjects will subsequently be withdraw

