	
made out of natural [animal] membrane [for example, polyurethane]; PLUS one additional barrier method: (a) diaphragm with spermicide; (b) cervical cap with spermicide; or (c) contraceptive sponge with spermicide.
 
OR
 

1. Option 3: Abstinence from sex when it is a lifestyle choice, and not just a social circumstance.

 
Exclusion Criteria
 

1. Subject is not able to provide written, informed consent and comply with the study protocol.

2. Subject is less than 18 years of age.

3. Subject has non-plaque type psoriasis on the hands and/or feet.

4. Patient does not have any evidence of psoriasis elsewhere.

5. Subject has concurrent cutaneous disease affecting the hands and/or feet that would interfere with assessments.

6. Subject has a ppPGA < 3 at screening/baseline visit.

7. Subject refuses to discontinue concomitant prescription medications on hands and/or feet.

8. Subject has used prescription topical treatments or received phototherapy treatment for psoriasis within 2 weeks of screening/baseline visit.

--	--

	

9. Subject has used intralesional kenalog within 4 weeks of screening/baseline visit.

10. Subject has taken oral treatments for psoriasis within 4 weeks of screening/baseline visit.

11. Subject has received any treatment with biologic medications within 5 half-lives (if known) or 16 weeks prior to screening/baseline, whichever is longer.

12. Subject refuses to use adequate birth control during the duration of the study period.

13. Subject is currently pregnant or breastfeeding.

--	--

Study Treatment	Duobrii® (halobetasol propionate 0.01%/tazarotene 0.045% lotion), thin layer applied to affected areas of palms and/or soles once a day
Study Duration	The total duration of study activities is 24 weeks
Schedule of Efficacy and Safety Assessments	Screening/Baseline (Week 0), Week 2, Week 8, Week 12, Week 16, Week 24
Laboratory Work	None
Safety Evaluations	Safety and tolerability will be assessed by adverse events, physical examinations (including skin examinations and ppPGA scoring), and concomitant medication review

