Statistical Analysis	Assuming the 40% of patients achieve ppPGA of 0 or 1 (similar to that seen with secukinumab) at week 24, this study requires 22 patients with a statistical power of 0.8 and 5% type one error
Budget Estimate	
\$120,845
 
88 tubes of Duobrii® (4 tubes of Duobrii® for each subject) supplied by Ortho Dermatologics.
 
The medication will be dispensed to the subject at week 0,2,8,16 and returned by the

	
subject at week 2,8,16,24.
 
Subjects will be compensated \$40 per study visit for their time and effort in participating in this study.

--	--

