## **Study Treatments**

Upon enrollment in the study, each subject will be given a supply of HP/TAZ at visits 0,2,8,16 to be used over the 24 weeks. Each subject will be instructed to apply a thin layer HP/TAZ to affected areas of palms and/or soles once a day for the duration of the study (i.e. daily treatment for 24 weeks).

All study treatments will be completed by the subject and will occur in the home setting. Subjects will be encouraged to record and report any missed treatments. Patients will be allowed to use OTC moisturizers, but should not apply them the days of their visits.

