## **Study Procedures & Guidelines**

The study is designed to include six study visits over 24 weeks. The procedures performed at each study visit are detailed below. All procedures will be performed at the single study site. They will also be instructed to store the investigational drug at 20 to 25 °C (68 to 77 °F), and to not freeze the drug.

A table detailing the study procedures is found in Appendix 1. All study visits and procedures will be documented in source documents created specifically for this study that will be completed in accordance with Good Clinical Practice (GP) documentation principles (i.e. attributable, legible, contemporaneous, original, accurate, enduring, available and accessible, complete, consistent, credible, and corroborated).

- I. Week 0 (Screening/Baseline)
  - A. Review Inclusion/Exclusion criteria
  - B. Obtain written informed consent
  - C. Review medical history and previous failed therapies

- D. Review concomitant medications
- E. Perform physical examination
- F. Obtain urine pregnancy test (for pre-menopausal female subjects only)
- G. Evaluate ppPGA
- H. Obtain photographs of affected areas
- I. Dispense study drug

II. Week 2

- A. Review adverse events
- B. Review concomitant medications
- C. Evaluate ppPGA
- D. Administer DQLI
- E. Administer NRS for treatment satisfaction
- F. Obtain photographs of affected areas
- G. Dispense study drug
- H. Collect study drug

III. Week 8

- A. Review adverse events
- B. Review concomitant medications
- C. Evaluate ppPGA
- D. Administer DQLI
- E. Administer NRS for treatment satisfaction
- F. Obtain photographs of affected areas
- G. Dispense study drug
- H. Collect study drug

IV. Week 12

- A. Review adverse events
- B. Review concomitant medications
- C. Evaluate ppPGA
- D. Administer DQLI
- E. Administer NRS for treatment satisfaction
- F. Obtain photographs of affected areas

V. Week 16

- A. Review adverse events
- B. Review concomitant medications
- C. Evaluate ppPGA
- D. Administer DQLI

- E. Administer NRS for treatment satisfaction
- F. Obtain photographs of affected areas
- G. Dispense study drug
- H. Collect study drug

VI. Week 24

- A. Review adverse events
- B. Review concomitant medications
- C. Evaluate ppPGA
- D. Administer DQLI
- E. Administer NRS for treatment satisfaction
- F. Obtain photographs of affected areas
- G. Collect study drug

VII. Early Termination

- A. Review adverse events
- B. Review concomitant medications

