## Appendix 1: Evaluation Schedule

Visit	Wk 0 Screening/ Baseline	Wk 2	Wk 8	Wk 12	Wk 16	Wk 24/ Early Termina- tion
Inclusion/Exclusion criteria	X					
Informed consent	X					
Review medical history, including previous and concomitant therapies	X					
Adverse events		X	X	X	X	X
Review con meds	X	X	X	X	X	X
Physical examination	X					X**
Urine pregnancy test*	X					
ppPGA	X	X	X	X	X	X
DLQI		X	X	X	X	X
NRS for treatment satisfaction		X	X	X	X	X
Photography	X	X	X	X	X	X
Dispense drug	X	X	X			X
Collect Drug		X	X		X	X

\*Urine pregnancy test is required for pre-menopausal female subjects only.

\*\*Physical examination is only required for early termination

ppPGA: Palmoplantar Physician Global Assessment is based on the Investigators Global Assessment (IGA) modified version 2011, specifically applied to the palms and soles and consisting of a 5-point scale: 0 (clear), 1 (almost clear/minimal), 2 (mild), 3 (moderate), 4 (marked/moderate-to-severe), 5 (severe).

DLQI: Dermatology Quality of Life Index is a 10 question dermatology-specific quality of life questionnaire.

NRS for treatment satisfaction: Numerical Rating Scale consisting of 1 question: "Consider all the good and bad things about this treatment. Overall, how satisfied are you with the treatment?" Answer options: -3 (very dissatisfied), -2 (moderately satisfied), -1 (mildly satisfied), 1 (mildly satisfied), 2 (moderately satisfied), 3 (very satisfied)

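### A drug contraindicated in pregnancy is re-dispensed to continuing pre-menopausal women at Weeks 2, 8 and 16 with no pregnancy test after Week 0

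*Combined protocol and SAP*

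**What the plan says.** Adverse Effects and Reporting gives the hazard: "HP/TAZ contains tazarotene, which is a teratogenic substance". From this it derives the contraindication and the entry test: "HP/TAZ is contraindicated in pregnancy and in this study, all pre-menopausal female subjects must have a negative pregnancy test before enrolling".

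Study Treatments sets the supply schedule: "each subject will be given a supply of HP/TAZ at visits 0,2,8,16 to be used over the 24 weeks". The Budget Estimate row of the Protocol Synopsis agrees: "The medication will be dispensed to the subject at week 0,2,8,16". The visit lists in Study Procedures & Guidelines also place dispensing at Weeks 0, 2, 8 and 16.

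In those visit lists the urine pregnancy test is item F at Week 0 and appears in none of the lists for Weeks 2, 8, 12, 16 and 24. Appendix 1 marks it once, in the Week 0 column. The footnote there, "Urine pregnancy test is required for pre-menopausal female subjects only", defines who is tested and adds no visit. The synopsis row on safety evaluations adds none either: "Safety and tolerability will be assessed by adverse events, physical examinations (including skin examinations and ppPGA scoring), and concomitant medication review".

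One later test exists. The early-termination list under Protocol Violations includes it, but that visit is for subjects who are leaving the study.

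The plan has other safeguards. Inclusion criterion 6 and exclusion criterion 12 require birth control throughout, exclusion criterion 13 bars current pregnancy, and a pregnancy during the study must be reported within 7 days of the information being received and the subject withdrawn.

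**The concern.** The plan's own reasoning runs from teratogenic component to contraindication to negative test before the drug is given. That reasoning applies as much to each new supply as to the first, because a Week 0 result says nothing about conception after Week 0. The plan applies it once and dispenses four times.

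After Week 0, detection in a continuing woman depends on what she knows and reports. Adverse-event and medication reviews may bring out a known pregnancy or a contraceptive lapse. Concomitant Therapies also implies a medical-history review at every visit, although the visit lists and Appendix 1 give history at Week 0 only for continuing subjects. None of these can find a pregnancy she is unaware of, and the report-and-withdraw rule starts only when the information arrives.

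At stake is avoidable fetal exposure to a drug that the protocol itself contraindicates. The Background notes that thick skin on the hands and feet reduces penetration of topical agents, but the plan does not relax the contraindication on that ground.

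**Working it through.** There is no plan figure to reproduce here. The check sets the testing schedule beside the dispensing schedule for a pre-menopausal woman who completes the study. Dispensing weeks come from Study Treatments, the synopsis and the visit lists; tests come from the visit lists and Appendix 1; treatment ends at Week 24.

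| Visit | Pregnancy test | Drug dispensed | Weeks until next supply or end of treatment |
|---|---|---|---|
| Week 0 | yes | yes | 2 − 0 = 2 |
| Week 2 | no | yes | 8 − 2 = 6 |
| Week 8 | no | yes | 16 − 8 = 8 |
| Week 12 | no | no | – |
| Week 16 | no | yes | 24 − 16 = 8 |
| Week 24 | no | no | – |

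1. **Supplies given without a test.** Three of four dispensings. Weeks covered: 6 + 8 + 8 = 22; 22/24 = 91.7%.
2. **Most treatment that a positive test could stop, if a detectable pregnancy is present.** Week 2: 24 − 2 = 22 weeks. Week 8: 24 − 8 = 16 weeks. Week 16: 24 − 16 = 8 weeks. These are upper limits; each assumes the pregnancy would otherwise have gone unnoticed to Week 24.
3. **Longest time from the last negative test to the end of the supply it covers.** As written: 24 − 0 = 24 weeks. With tests at Weeks 0, 2, 8 and 16: the maximum of 2, 6, 8 and 8, which is 8 weeks.
4. **Extra tests.** For n eligible completers, 3n. The documents do not give n, so the range 0 to 22 is assumed: n = 0, 5, 11, 22 gives 0, 15, 33, 66. With a Week 24 test as well, 4n gives 0, 20, 44, 88.

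**The Appendix 1 dispensing row.** In the text available for review, the last mark in the row "Dispense drug" falls under Week 24/Early Termination and not under Week 16. This is probably a table or extraction error. Nothing above depends on it, since the synopsis, Study Treatments and the visit lists all give Week 16.

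**The early-termination test.** It is listed under Protocol Violations but is absent from the early-termination list in Study Procedures & Guidelines and from the shared last column of Appendix 1. Staff who follow those two places would test no one after Week 0.

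**The case against.** The strongest reply is that the plan does what it promises. It requires a negative test before enrolment and schedules one, and no document sets a retest interval. That is right: this is an omission, not a contradiction, and the choice of retest visits is a proposal.

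Second, prevention is already strong. Several permitted methods, such as an intrauterine device, an implant or tubal ligation, do not depend on daily behaviour once in place. This also stands, and it lowers the risk. But the plan equally permits a condom with a second barrier method, or abstinence, and no later visit list checks that the method is still in use. The gap lies in detection, which prevention does not supply.

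Third, the 92% is a share of the schedule and not a risk. Agreed. The 22-week figure is likewise an extreme, since it needs a pregnancy detectable at Week 2, two weeks after a negative test, and otherwise unnoticed to the end.

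Fourth, Week 12 is also an existing visit, and a positive test there could stop treatment. It would split the Week 8 to 16 interval into 12 − 8 = 4 and 16 − 12 = 4 weeks. It is a reasonable extra, but no drug is dispensed then, and the longest interval would remain 8 weeks because of Weeks 16 to 24.

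None of these points supplies a test before a new supply is handed over.

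**Conclusion.** The concern holds and should be fixed. As scheduled, a continuing pre-menopausal woman has one test and then three re-supplies without one. The finding rests on the dispensing weeks given consistently in three places in the text, and on the absence of a test from every later visit list and from Appendix 1.

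No probability of exposure is claimed. The consent pages were not available, so the conclusion concerns scheduled tests only and not the instructions given to subjects. Confidence in the missing tests is high; the exact retest visits are a matter of judgement. The harm would be serious and the remedy is small, which justifies an amendment even in a study of 22 subjects with mandatory contraception.

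**What to change.** In Study Procedures & Guidelines and in Appendix 1:

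- Add a urine pregnancy test at Weeks 2, 8 and 16 for the same group as at Week 0, with a negative result required before drug is dispensed. These are the visits after Week 0 at which a new supply can be withheld.
- If the result is positive, collect the drug and apply the existing report-and-withdraw rule.
- At each visit, ask one contraception question: is the method still in use, and has there been any lapse?

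Secondary changes:

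- Make the two early-termination lists and Appendix 1 agree that the test is done at early termination.
- Consider a Week 24 test, which documents exposure in completers but does not prevent it.
- Check the Appendix 1 dispensing mark against the source table and place it at Week 16.

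The cost is a protocol and schedule amendment, plus three urine tests (four with Week 24) and a few minutes per eligible completer. The ceiling is 66 tests, or 88 with Week 24. The visits already take place, the test is already used at Week 0, and Data Collection, Retention, & Monitoring already lists its result among the data collected.

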## Protocol Violations

Subjects may withdraw from the trial at any time at their request (verbal or written), or they may be withdrawn at any time at the discretion of the Sponsor, PI, or designee for safety, behavioral, or administrative reasons. Subjects may be withdrawn from this study without their consent if the research study is being stopped; or if the instructions of the study team have not been followed.

Any enrolled subject who will not be completing the duration of the study will be asked to complete an Early Termination study visit, consisting of the procedures indicated below. In addition, the reason for Early Termination will be recorded in the source documents.

- 1) Review medical history
- 2) Review concomitant medications
- 3) Perform physical examination
- 4) Obtain urine pregnancy test (for pre-menopausal female subjects only)
- 5) Evaluate ppPGA
- 6) Administer DQLI

- 7) Administer NRS for treatment satisfaction
- 8) Obtain photographs of affected areas

If a subject is unable or unwilling to complete an Early Termination visit, this will be documented in the source documents.

## Statistical Methods & Considerations

Assuming the 40% of patients achieve ppPGA of 0 or 1 (similar to that seen with secukinumab) at week 24, this study requires 22 patients with a statistical power of 0.8 and 5% type one error.

Post-trial statistics of the data will be assessed by an individual that's not part of the study staff.

## Data Collection, Retention, & Monitoring

Data collected during this study will include: patient demographic information, past medical history, adverse events, concomitant medication, physical exam findings, urine pregnancy test results (for pre-menopausal female subjects only), ppPGA evaluations, DLQI evaluations, NRS for treatment satisfaction evaluations, and serial photography of affected areas. These data will be stored on-site, with the source documents in a secure, locked physical location and the electronic data in a password-protected format.

Access to this data will be limited to study staff. All study staff will be trained on how to maintain the security of the data via limited authorization of access, password protection, encryption, physical controls, and separation of identifiers and data.

This data will be stored on-site for a minimum of 10 years following completion of all study activities.

## Ethical & Regulatory Considerations

**Consent process:** Consent discussions will occur in a private setting. The consent process will be initiated well in advance to ensure that subjects have sufficient opportunity to consider participation.

The consent process will be enforced per SOP HRP-090 Informed Consent Process for Research. Individuals listed in the application are authorized to obtain consent. However, to minimize undue influence and to allocate ample time for discussion, the consent responsibility will be delegated to the dermatology clinical trial research team.

No children (i.e. subjects under the age of 18) or cognitively impaired adults (i.e. adults who may be unable to consent) will be enrolled in this study.

Consent of the subjects will be documented in writing per the standard PPHS consent template.

**Sharing of results:** Results of this study will not be shared with subjects or others who are not directly involved in the study (e.g. subjects' primary care physicians).

**Specimen banking:** No specimens will be banked in association with this study.

**External IRB Review History:** This protocol has not been previously submitted to an external IRB.

**Control of drugs:** The investigational drug will be stored at 20 to 25 °C (68 to 77 °F) in a secure, locked on-site location that is accessible only by authorized investigators involved in the study.

**Publication of study findings:** The findings in this study will result in at least one poster at a conference and at least one publication.

# Figure 1: Patient-Reported Outcomes instrument

## DERMATOLOGY LIFE QUALITY INDEX (DLQI)

The aim of this questionnaire is to measure how much your skin problem has affected your life OVER THE LAST WEEK.  
Please check one box for each question.

1.	Over the last week, how itchy, sore, painful or stinging has your skin been?	Very much A lot A little Not at all	   	
2.	Over the last week, how embarrassed or self conscious have you been because of your skin?	Very much A lot A little Not at all	   	
3.	Over the last week, how much has your skin interfered with you going shopping or looking after your home or yard ?	Very much A lot A little Not at all	   	Not relevant 
4.	Over the last week, how much has your skin influenced the clothes you wear?	Very much A lot A little Not at all	   	Not relevant 
5.	Over the last week, how much has your skin affected any social or leisure activities?	Very much A lot A little Not at all	   	Not relevant 
6.	Over the last week, how much has your skin made it difficult for you to do any sport ?	Very much A lot A little Not at all	   	Not relevant 

7.	Over the last week, has your skin prevented you from working or studying ?	yes no	 	Not relevant 
	If "No", over the last week how much has your skin been a problem at work or studying ?	A lot A little Not at all	  	
8.	Over the last week, how much has your skin created problems with your partner or any of your close friends or relatives ?	Very much A lot A little Not at all	   	Not relevant 
9.	Over the last week, how much has your skin caused any sexual difficulties ?	Very much A lot A little Not at all	   	Not relevant 
10.	Over the last week, how much of a problem has the treatment for your skin been, for example by making your home messy, or by taking up time?	Very much A lot A little Not at all	   	Not relevant 

Please check you have answered **EVERY** question. Thank you.

Source: Finlay AY, Khan GK. Dermatology Life Quality Index (DLQI)--a simple practical measure for routine clinical use. *Clin Exp Dermatol*. 1994;19(3):210-216.

